## 2. INVESTIGATIONAL PLAN

### 2.1. Study Objectives

#### 2.1.1. Primary Efficacy Objective:

The primary study endpoint will be a rating of disease severity on Day 28, or last rating evaluated, using a seven-category severity scale:

1. Not hospitalized, negative PCR for SARS-CoV-2
2. Not hospitalized, positive PCR for SARS-CoV-2 without symptoms
3. Not hospitalized, positive PCR for SARS-CoV-2 with symptoms
4. Non-ICU hospitalization, not requiring supplemental oxygen
5. Non-ICU hospitalization, requiring supplemental oxygen
6. Requiring mechanical ventilation and/or in ICU
7. Death

Time to various dichotomizations on the severity scale will be assessed

#### 2.1.2. Primary Safety Objective:

To evaluate the safety of anti- SARS-CoV-2 plasma versus control (albumin 5%)

#### 2.1.3. Secondary Objectives:

1. To compare the anti-SARS-CoV-2 titers between the recipients of anti-SARS-CoV-2 plasma versus control (albumin 5%) at days 3, 7, 14, 28 and 90
2. To compare the proportion and duration of SARS-CoV-2 PCR positivity (RT-PCR) between the recipients of the anti-SARS-CoV-2 plasma versus control (albumin 5%) at days 0, 3, 7, 14 and 28
3. To compare the levels of SARS-CoV-2 RNA between the recipients of anti-SARS-CoV-2 plasma and control (albumin 5%) at days 0, 3, 7, 14 and 28

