A general principle of passive antibody therapy is that it is more effective when used for prophylaxis than for treatment of disease. When used for therapy, antibody is most effective when administered shortly after the onset of symptoms. The reason for temporal variation in efficacy is not well understood but could reflect that passive antibody works by neutralizing the initial inoculum, which is likely to be much smaller than that of established disease. Another explanation is that antibody works by modifying the inflammatory response, which is also easier during the initial immune response, which may be asymptomatic (Casadevall & Pirofski, 2003).

As an example, passive antibody therapy for pneumococcal pneumonia was most effective when administered shortly after the onset of symptoms and there was no benefit if antibody administration was delayed past the third day of disease (Casadevall & Scharff, 1994).

For passive antibody therapy to be effective, a sufficient amount of antibody must be administered. When given to a susceptible person, this antibody will circulate in the blood, reach tissues and provide protection against infection. Depending on the antibody amount and composition, the protection conferred by the transferred immunoglobulin can last from weeks to months.

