## 1.2. Overview of known potential risks

Historical and current anecdotal data on use of convalescent plasma suggest it is safe in coronavirus infection. Therefore, the large number of exposed healthcare workers, public servants and first responders, in combination with the high mortality of COVID-19, particularly in elderly and vulnerable persons, strongly argue that the benefits of convalescent serum outweigh its possible risks in high risk exposed individuals and/or those with early disease. However, for all cases where convalescent plasma administration is considered, a risk-benefit assessment must be conducted to assess individual variables.

The theoretical risk involves the phenomenon of antibody-mediated enhancement of infection (ADE). ADE can occur for several viral diseases and involves an enhancement of disease in the presence of certain antibodies. For coronaviruses, several mechanisms for ADE have been described and there is the theoretical concern that antibodies to one type of coronavirus could enhance infection to another viral strain (Wan et al., 2020). It may be possible to predict the risk of ADE of SARS-CoV-2 experimentally, as proposed for MERS. Since the proposed use of convalescent plasma in the COVID-19 epidemic would rely on preparations with high titers of neutralizing antibody against the same virus, SARS-CoV-2, ADE may be unlikely. The available evidence from the use of convalescent plasma in patients with SARS1 and MERS (Mair-Jenkins et al., 2015), and anecdotal evidence of its use in patients with COVID-19 (Xinhua, 2020), suggest it is safe. Nevertheless, caution and vigilance will be required in for any evidence of enhanced infection.

Another theoretical risk is that antibody administration to those exposed to SARS-CoV-2 may avoid disease but modify the immune response such that those individuals mount attenuated immune responses, which would leave them vulnerable to subsequent re-infection. In this regard, passive antibody administration before vaccination with respiratory syncytial virus was reported to attenuate humoral but not cellular immunity (Crowe, Firestone, & Murphy, 2001). This concern will be investigated as part of this clinical trial by measuring immune responses in those exposed and treated with convalescent plasma to prevent disease. If the concern proved real these individuals could be vaccinated against COVID-19 when a vaccine becomes available.

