**Table: Schedule of Events**

Study period	Screen	Baseline	Infusion	Follow up						
Day	-1 to 0	0	0	1	3±2	7±1	14±3	28±7	60±7	90±7
Eligibility										
Informed consent	x									
Demographic and Medical history	x									
COVID-19 symptom screen	x		x							
SARS-CoV-2 ID NOW and RT-PCR obtained for eligibility	x 									
Pregnancy test 	x									
ABO 	x									
Study Drug Administration										
Randomization		x								
Drug infusion			x							
Study Procedures										
COVID-19 Symptom screen	x		x	x	x	x	x	x	x	
Other symptoms screen	x		x	x	x	x	x	x	x	
Concomitant medications	x		x	x	x	x	x			
Vital signs	x		x 		x	x	x			
Targeted physical examination	x		x			x	x			

 A repeat ID NOW and PCR at screening is required for all participants. However, for participants with documented evidence of infection by nasal swab PCR that is positive for SARS-CoV-2 in the prior week, a positive swab is not required to enroll the participant since they were already positive in the past week and will be tested by PCR during the Infusion Visit. At screening, two swabs will be collected from each participant, one for ID NOW (or comparable rapid antigen test) and one for a PCR-based test. If ID NOW is positive, it will not be necessary to wait for the PCR based test result to confirm the positive. If the ID NOW is negative, it will be necessary to wait for the PCR test result: PCR negative will mean individual is not eligible and PCR positive will mean they are potentially eligible if all the other inclusion criteria are met.

 Urine pregnancy test for women of childbearing potential

 Assessment of ABO type on file; requires two tubes of blood drawn 5 minutes apart, as per NYP Blood Bank procedures

 Vital sign testing: Immediately prior to infusion, 10-20 minutes after start of infusion, at completion of infusion and 15-60 minutes after the end of the infusion

Study period	Screen	Baseline	Infusion	Follow up						
Day	-1 to 0	0	0	1	3±2	7±1	14±3	28±7	60±7	90±7
Assessment of composite outcome of disease severity 			x	x	x	x	x	x	x	
Adverse event monitoring			x	x	x	x	x	x	x	
Laboratory testing										
CBC and CMP 	x					x	x			
SARS-CoV-2 RT-PCR 	x		x		x	x	x	x		
SARS-CoV-2 antibody	x				x	x	x	x		x
Blood for future testing	x				x	x	x	x		
Viral culture 	x				x					

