### 2.3.5 Stratified Randomization

1. Subjects enrolled in the study will be stratified and randomized using an interactive web- based system

 Assessment evaluates whether subject has shifted from “no clinical or laboratory evidence of COVID-19 infection to any of the composite outcomes of disease severity

[figure not shown]
 Comprehensive metabolic panel

 Nasal swab

 Includes sequencing for viral variants

 10 % sample of the nasal swabs

2. Subjects will be stratified by steroid administration (prior oral or IV steroids within prior 2 weeks at time of enrollment or prior inhaled steroids within prior 24 hours at time of enrollment) and by vaccination status (prior COVID-19 vaccine at time of enrollment) and then randomized in a 2:1 ratio to either CP or albumin 5%

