#### **4.10 Day 90 ± 7**

1. Serological testing: anti-SARS-CoV-2 titers

+ In order to minimize exposure to SARS-CoV-2 virus, at the clinician's discretion, face to face interactions may be minimized by collecting information by phone or by telemedicine (Zoom HIPAA compliant conferencing)

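### COVID-19 vaccination after Day 14 is not scheduled for collection, so the Day 90 titer comparison, the most usable check for an attenuated immune response, cannot be checked or adjusted for it

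*Combined protocol and SAP*

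**What the plan says.** Section 1.2 raises the risk that passive antibody leaves recipients with a weaker response of their own and open to re-infection. It then commits the trial: "This concern will be investigated as part of this clinical trial by measuring immune responses in those exposed and treated with convalescent plasma". It adds a possible consequence: "If the concern proved real these individuals could be vaccinated against COVID-19 when a vaccine becomes available".

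The matching measurement is the first secondary objective in Section 2.1.3: "To compare the anti-SARS-CoV-2 titers between the recipients of anti-SARS-CoV-2 plasma versus control (albumin 5%) at days 3, 7, 14, 28 and 90". Sections 3.1 and 5.3 repeat those days. In the Schedule of Events, blood for PBMC is taken at screening only. Stored blood ends at Day 28 and has no immune analysis assigned to it.

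On infused antibody, Section 2.4.4 expects a recipient titer of 1:45 from the infusion, and Section 1 says "the protection conferred by the transferred immunoglobulin can last from weeks to months". No half-life is given.

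On vaccination, Section 2.3.5 stratifies "by vaccination status (prior COVID-19 vaccine at time of enrollment", so vaccines were already in use. After enrollment no vaccination item is named anywhere. The schedule row "Concomitant medications" is marked at screening, infusion and Days 1, 3, 7 and 14, and not at Days 28, 60 or 90. The Section 4 visit lists mention concomitant medication on Day 0 and not afterwards. At Days 28 and 60 they ask about symptoms, clinical status, new medical conditions and adverse events. Section 4.10 gives one item for Day 90: "Serological testing: anti-SARS-CoV-2 titers".

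Section 3.2 assigns longitudinal data to generalized linear mixed models with 95% confidence intervals. It does not say which time point answers the attenuation question, or how infused antibody or vaccination during follow-up is handled.

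**The concern.** Infused antibody can only raise plasma-arm titers. If the recipient's own response is weakened, the infusion can fill the gap at Days 3 to 28, and similar or higher titers would look reassuring when they are not. By Day 90 most infused antibody should be gone, which makes that sample the one best suited to the question in Section 1.2.

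That sample is also the one most exposed to vaccination during follow-up. A participant vaccinated on Day 40 would appear at Day 90 with a high titer and nothing in the scheduled data to explain it. The same applies to convalescent plasma or an antibody product given outside the study after Day 14. Vaccine-induced antibody adds spread in both arms and may shrink the difference between them. Both effects push towards a finding of no attenuation. The final analysis plan can still set handling rules before unblinding, but it cannot apply them to dates that were not collected.

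**Working it through.** **The plan's own figure.** Inputs from Section 2.4.4: titer 1:320, 500 mL infused, plasma volume 3,500 mL. 320 × 500 / 3500 = 45.7, stated as 1:45. It reproduces. With 400 mL, the lower end of the planned volume, 320 × 400 / 3500 = 36.6, about 1:37.

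**Infused antibody remaining.** Assumption: half-life h of 14 to 28 days. Remaining titer = 45 × 0.5^(t/h).

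| Day | Share left | Titer from infusion alone |
|---|---|---|
| 3 | 86-93% | 1:39 to 1:42 |
| 7 | 71-84% | 1:32 to 1:38 |
| 14 | 50-71% | 1:23 to 1:32 |
| 28 | 25-50% | 1:11 to 1:23 |
| 90 | 1-11% | 1:5 or less |

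The infusion still contributes materially at Day 28 and little at Day 90.

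**Power at Day 90.** From Section 3.1: 100 plasma, 50 control. Assumptions, since the documents give none of these: true attenuation of 1 log2 step (twofold), SD 2 log2 (range 1.5 to 2.5), a fraction v vaccinated equally in both arms, a vaccine boost b of 2 to 3 log2 (4- to 8-fold), nobody vaccinated before enrollment and no missing samples. The test is two-sided at 5%, to match the 95% intervals in Section 3.2.

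Power = Φ(difference / SE − 1.96), with SE = SD × √(1/100 + 1/50) = SD × 0.1732.

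Nobody vaccinated, SD 2: SE = 0.346; 1/0.346 = 2.89; power = Φ(0.93) = 82%.

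With vaccination, variance per arm = SD² + v(1 − v)b². For v = 0.4, SD 2:

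- b = 2: variance 4 + 0.24 × 4 = 4.96, SE 0.386.
- b = 3: variance 4 + 0.24 × 9 = 6.16, SE 0.430.
- Attenuation persists after vaccination (difference 1.0): Φ(0.63) = 74% and Φ(0.37) = 64%.
- Vaccination erases the difference (difference 0.6): Φ(−0.40) = 34% and Φ(−0.56) = 29%.

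If vaccination brings both arms to the same level, the plasma arm has the larger jump (b + 1). Its variance is then 6.16 (b = 2) or 7.84 (b = 3), and power is 32% and 27%. The erased case therefore spans about 27-34%.

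| SD (log2) | None vaccinated | 40%, attenuation persists | 40%, attenuation erased (common variance) |
|---|---|---|---|
| 1.5 | 97% | 79-90% | 38-49% |
| 2 | 82% | 64-74% | 29-34% |
| 2.5 | 64% | 51-58% | 22-25% |

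**Leaving out post-vaccination samples.** At v = 0.4, 60 and 30 samples remain: SE = 2 × √(1/60 + 1/30) = 0.447; power = Φ(0.28) = 61%, with the full 1.0 log2 difference. That beats 27-34% but falls short of 64-74%. Exclusion helps in one case and costs power in the other.

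**Unequal uptake.** A 20-point difference in uptake would shift the contrast by 0.2 × 2 = 0.4 to 0.2 × 3 = 0.6 log2. The scheduled data could not show whether that had happened.

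**The case against.** The case on the other side is substantial, and several parts of it stand.

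- A reader might infer that vaccination is never recorded. That goes too far. Status at enrollment is a stratification factor, and a dose given by Day 14 could appear under concomitant medications.
- A reader might infer that Day 90 cannot answer the question at all. The arms are randomized, blinded and stratified by prior vaccination, and the documents give no reason to expect different uptake. With similar uptake the comparison remains valid, though noisier and possibly diluted.
- A reader might infer that early titers say nothing about the recipient's own response. Because infusion can only raise the plasma arm, a plasma-arm titer below control at Day 14 or 28 would be conservative evidence of attenuation. Only an equal or higher titer is ambiguous.
- Titers also have another purpose. Section 5 groups them with efficacy, virologic and PK measures, and for PK the infused antibody is the signal. The attenuation aim comes from one background sentence, which speaks of people treated to prevent disease, while the trial enrolls infected people. This weakens the link, but Section 1.2 still promises the investigation within this trial.
- Hospital records are source documents under Section 8.6.1 and locator forms are held, so some later tracing is possible. Neither is planned as a way to collect vaccination dates.
- Section 3.2 defers the final analysis plan. That covers the analysis rules but not the missing data item.

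The gap in collection after Day 14 survives all of these.

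**Conclusion.** The point holds in a limited form. Titers are the only planned immune measure after infusion. Those at Days 3 to 28 combine infused and own antibody, with no plan to separate them. Vaccination and non-study antibody products after Day 14 are not scheduled for collection, so the Day 90 comparison cannot be checked, adjusted or censored for them.

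In the illustration with SD 2 log2, twofold attenuation and 40% vaccinated, power drops from 82% to 64-74% or to 27-34%, depending on whether attenuation persists after vaccination. It would be tempting to quote only the lower range. The documents do not support that: whether vaccination erases the difference is an assumption, as are the half-life, SD, boost and uptake. The direction is firmer than the size. With balanced uptake, vaccination costs precision and may dilute the contrast towards no attenuation; bias needs unequal uptake.

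This concerns one secondary objective. The Day 28 severity rating and the go/no-go decision are untouched, so it is a cheap improvement and not a flaw in the main design.

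**What to change.** - At the existing Day 14, 28, 60 and 90 contacts, record the date of any COVID-19 vaccine dose and of any non-study plasma or antibody product. Add the item to the Schedule of Events and to Sections 4.7 to 4.10.
- In Section 3.2, name Day 90 as the time point for the attenuation question. Keep the randomized comparison of all samples as the main analysis.
- Report uptake of vaccine and non-study antibody products by arm.
- Prespecify a sensitivity analysis that censors or adjusts for titers taken after a vaccine dose or antibody product.
- Describe Day 3 to 28 titers as infused plus own antibody, and state that equal or higher plasma-arm values at those days do not exclude attenuation.

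The cost is one more CRF item at contacts that already take place and a few lines of analysis text. The sensitivity analysis conditions on an event after randomization, and censoring reduces the sample (60 and 30 at 40% uptake). For those reasons it should sit beside the all-samples comparison and not replace it.

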#### 2.1.4 Exploratory Objectives:

To assess the correlation between SARS-CoV-2 PCR positivity from nasal swab specimens, based on RT PCR, and detection of viable SARS-CoV-2 from nasal swab specimens based on viral culture assays.

---

 A nasopharyngeal (NP) or nasal mid-turbinate (NMT) swab, also called a Deep Nasal Swab (may be self-collected by each research subject as per CDC guidance; <https://www.cdc.gov/coronavirus/2019-ncov/lab/guidelines-clinical-specimens.html>) are both acceptable

## 2.2 Definitions

- I. Enrolled: from time consented to participate until designated as a screen failure or have been discontinued from the study or completed it.
- II. Randomized: when a randomization PTID number has been assigned
- III. Screen Failures: signed informed consent and received a screening PTID, but then determined to be ineligible or withdrew before being randomized
- IV. Discontinued: randomized, but then withdrawn by investigator or withdrew consent
- V. Completed: Subjects are considered completed when they are followed through to day 28 or if they die before day 28

## 2.3 Study population

### 2.3.1 Inclusion Criteria for Enrollment

1. Subjects must be 18 years of age or older
2. a. Recent close contact3\* with a person with COVID-19, i.e. last close contact occurred within 7 days of anticipated infusion of study product. It is anticipated that most contacts will be household contacts with extensive interaction. All must meet the CDC criteria for close contacts. This includes healthcare workers at higher risk of developing severe disease.  
OR  
b. Recent self-reported or documented evidence of infection by nasal swab ID NOW or PCR that is positive for SARS-CoV-2, i.e., nasal sample was collected within 7 days or 10 days of anticipated infusion of study product for those who are asymptomatic or symptomatic, respectively.
3. Evidence of infection by nasal swab ID NOW or PCR that is positive for SARS-CoV-2 at screening visit

---

 Close contact is defined by CDC as being within approximately 6 feet (2 meters) of a COVID-19 case for a prolonged period of time (without PPE); close contact can occur while caring for, living with, visiting, or sharing a healthcare waiting area or room with a COVID-19 case.

 7 days (if asymptomatic at prescreening) or 10 days (if minimally to moderately symptomatic during prescreening) are based on the number of days from specimen collection date to anticipated infusion date

 A repeat ID NOW and PCR at screening is required for all participants. However, for participants with documented evidence of infection by nasal swab PCR that is positive for SARS-CoV-2 in the prior week, a positive swab is not required to enroll the participant since they were already positive in the past week and will be tested by PCR during the Infusion Visit. At screening, two swabs will be collected from each participant, one for ID NOW (or comparable rapid antigen test) and one for a PCR-based test. If ID NOW is positive, it will not be necessary to wait for the PCR based test result to confirm the positive. If the ID NOW is negative, it will be necessary to wait for the PCR test result: PCR negative will mean individual is not eligible and PCR positive will mean they are potentially eligible if all the other inclusion criteria are met.

4. May or may not be hospitalized
5. No symptoms or no more than 7 days of moderate symptoms at the time of screening.

Moderate symptoms may include:

- a. Moderate rhinorrhea
- b. Moderate sore throat or throat irritation
- c. Moderate cough
- d. Moderate fatigue (may interfere with ability to perform ADLs)
- e. Moderate chills, measured temperature and/or feeling feverish, muscle pain

6. Calculated Risk Score for severe COVID-19 [based on CDC description] of 0 points if on supplemental oxygen at enrollment; otherwise Calculated Risk Score of  $\geq 1$ .
  - Age 65-74: 1 point
  - Age  $\geq 75$ : 2 points
  - Known cardiovascular disease (including hypertension): 1 point
  - Diabetes mellitus: 1 point
  - Pulmonary disease (COPD, moderate to severe asthma, current smoking or other): 1 point
  - Morbid obesity: 1 point
  - Immunocompromised state: 1 point  
Received a bone marrow or solid organ transplant at any time, received chemotherapy for a malignancy within the past 6 months, has an acquired or congenital immunodeficiency, currently receiving immunosuppressive or immune modulating medications, HIV with non-suppressed viral load and/or CD4+ T cell count  $<200$  cells/mL).
7. Those who do not require more than 4 LPM of supplemental oxygen at enrollment.

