## 3 STATISTICAL CONSIDERATIONS

### 3.1 Design Overview

This is a double-blinded, randomized phase 2 trial to evaluate the efficacy and safety of human SARS-CoV-2 immune plasma in individuals who are close contacts to person with COVID-19 within 7 days according to the CDC definition. This will also serve as an internal pilot in the seamless phase 2/3 study.

Eligible participants will be randomized to receive high-titer anti-SARS-CoV-2 immune plasma or control (albumin 5%) in a 2:1 ratio. We plan to enroll a total of 150 participants, with a maximum of 100 receiving the plasma and 50 receiving the control.

Each participant will be followed for 28 days after randomization and treatment, and will be tested and evaluated at baseline and on Days 3, 7, 14, 28 using a seven-category severity scale:

1. Not hospitalized, negative PCR for SARS-CoV-2
2. Not hospitalized, positive PCR for SARS-CoV-2 without symptom
3. Not hospitalized, positive PCR for SARS-CoV-2 with symptoms
4. Non-ICU hospitalization, not requiring supplemental oxygen
5. Non-ICU hospitalization, requiring supplemental oxygen
6. Requiring mechanical ventilation and/or in ICU
7. Death

The primary study endpoint is the rating on Day 28, or last rating evaluated. We will also consider time to various dichotomizations on this scale as secondary

outcomes, including time to death, time to requiring critical care, and time to requiring hospitalization

Other endpoints include:

- Anti-SAR-CoV-2 titers (Days 3, 7, 14, 28, 90 in addition to baseline)
- SAR-CoV-2 PCR positivity (Days 0, 3, 7, 14, 28 in addition to baseline)
- SAR-CoV-2 RNA (Days 0, 3, 7, 14, 28 in addition to baseline)

Exploratory objective:

- To assess the correlation between SARS-CoV-2 PCR positivity from nasal swab specimens, based on RT PCR, and detection of viable SARS-CoV-2 from nasal swab specimens based on viral culture assays

Serious adverse events, and grades  $\geq 3$  adverse events will be monitored during the study period.

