## 3.2 Statistical Analysis

Primary Analysis and go/no-go decision: The severity scale of the two groups will be compared using stratified, Mann Whitney test. Specifically, a one-sided  $P < 0.15$  favoring the immune plasma arm will constitute a “go decision” in this phase 2 trial, suggesting evidence of promise for further investigation in an expanded Phase 3 study. The results in this trial will then be used to plan the Phase 3 sample size, with possibility that the data in this Phase 2 trial will be included in the final analysis using adjusted  $P$  values. Details of sample size re-estimation and adjusted analysis, as well as the final statistical analysis plan, will be determined before unblinding the study data.

This analysis will be intent-to-treat. Given the short study duration and the nature of the treatment, however, we anticipate minimal non-compliance and loss to follow-up.

Subgroup Analysis: If the stratified analysis reaches the go decision, with  $P < 0.15$ , we will explore the treatment effect within each stratum using Mann Whitney test.

Secondary Analyses: All secondary efficacy analyses will be intent-to-treat. Time-to-event variables (e.g. time to death) will be analyzed using Cox proportional hazard model. Longitudinal data collected over multiple days (e.g., PCR positivity) will be analyzed using generalized linear mixed models. Treatment effects on these variables will be estimated with 95% confidence intervals.

Safety Analyses: Serious adverse events will be summarized by grades and types using proportions and 95% confidence intervals for the two study arms, and the two arms will be compared using Fisher's exact test.

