### 3.3 Power Consideration

Assuming a shift odds ratio of 2 under a proportional odds model on the severity rating scale, with a sample size of 150, the study will have 74% to 80% power of reaching the go decision in the scenarios we considered. The actual power will depend the distribution of the severity scale in the control arm. Table 2 gives the power of the two extreme scenarios: Scenario 1 describes scenario with higher rates for more severe outcomes, and Scenario 2 with majority of participants remaining or becoming PCR negative; the outcome distributions are identical between the two strata in these scenarios. We have evaluated the power for in-between scenarios and scenarios where non-infected and infected strata are different; the power is within the range 74% and 80% in all scenarios we have considered.

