## **7.3 Halting Criteria for the Study**

The study enrollment and dosing will be stopped and an ad hoc review will be performed if any of the specific following events occur or, if in the judgment of the study physician, subject safety is at risk of being compromised:

1. Unexpected death of a dosed subject in relation to infusion
2. Occurrence of a life-threatening allergic/hypersensitivity reaction (anaphylaxis), manifested by bronchospasm with or without urticaria or angioedema requiring hemodynamic support with pressor medications or mechanical ventilation.
3. One subject with an unexpected SAE associated with study product.
4. Two subjects with a Grade 3 or higher toxicity for the same parameter associated with study product.
5. An overall pattern of symptomatic, clinical, or laboratory events that the DSMB consider associated with study product and that may appear minor in terms of individual events but that collectively may represent a serious potential concern for safety.
6. Any other event(s) which is considered to be a serious adverse event in the good clinical judgment of the responsible physician. This will be appropriately documented.

Furthermore, given that ADE may be an issue with convalescent antibody treatment, out of an abundance of caution we will monitor the number of subjects in each trial arm that progresses to an indication for need of mechanical ventilation. In monitoring the number of subjects that progresses to this stage, we will present these data to the DSMB masked so that they may objectively evaluate and determine whether they would like to be unmasked. After at least 50% of trial participants have accumulated follow-up, the number of subjects that progress to this stage will be presented to the masked DSMB and formally asked whether they (1) see a clinically meaningful difference between trial arms that trigger an unmasking of the

DSMB and (2) if so do they require a formal interim analysis. At any point should the DSMB asked to be unmasked and require a formal interim analysis, we will examine the difference in treatment arms for need for mechanical ventilation. This interim analysis will adjust for factors related to need for mechanical ventilation including age and presence of cardiopulmonary comorbidities.

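### The graded baseline risk score is used only for entry. The go/no-go test leaves it out, at a modest, assumption-dependent cost in power and in protection against chance risk imbalance

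*Combined protocol and SAP*

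**What the plan says.** Section 2.3.1 item 6 defines the "Calculated Risk Score for severe COVID-19". It gives one point for age 65-74, two for 75 and over, and one each for cardiovascular disease, diabetes, pulmonary disease, morbid obesity and immunocompromise. Entry needs at least 1 point, except that a person on supplemental oxygen may enter with 0. Section 2.3.3.2 repeats this as a pre-screening check. The score is not used again.

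Section 2.3.5: "Subjects will be stratified by steroid administration" and by prior COVID-19 vaccination, then randomized 2:1. Section 3.1: "We plan to enroll a total of 150 participants, with a maximum of 100 receiving the plasma and 50 receiving the control".

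Section 3.2: "The severity scale of the two groups will be compared using stratified, Mann Whitney test". A one-sided P below 0.15 "favoring the immune plasma arm will constitute" a go decision. The section names no covariate and does not name the strata. Section 3.3 mentions "scenarios where non-infected and infected strata are different", which are not the factors of Section 2.3.5. Neither set is a measure of age or comorbidity. The final analysis plan is left to be settled before unblinding.

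Section 7.3 provides for an analysis of mechanical ventilation if the DSMB asks to be unmasked and requires one: "This interim analysis will adjust for factors related to need for mechanical ventilation including age and presence of cardiopulmonary comorbidities".

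**The concern.** The protocol itself treats age and cardiopulmonary disease as related to ventilation, and the primary scale has ICU or ventilation and death as its two worst categories. Yet the adjustment is reserved for an interim look that may never take place, and the decision the trial exists to make goes without it.

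Two things are at stake. First, any outcome variation that baseline risk explains stays in the noise, which lowers power. Second, with 100 against 50 participants and no balancing on risk, the arms will differ somewhat by chance. A reader of the actual result could not tell how far a go, or a no-go, reflects that difference. The decision also matters beyond this trial: Section 3.2 uses the data to size Phase 3 and may carry them into its final analysis.

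**Working it through.** **Inputs from the documents.** 100 plasma and 50 control; one-sided 0.15 (critical value 1.036); shift OR 2; the control columns of Table 2 (Section 3.3).

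**Assumptions, because the documents are silent.** Score levels 1/2/3 in 50/30/20% of entrants, or 1/2/3/4 in 50/30/15/5%; OR for worse severity per point between 1.25 and 3.

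**1. The plan's power.** Power = Φ(ln OR × √V − 1.036), with V = n₁n₂N / [3(N+1)²] × (1 − Σp̄³), where p̄ is the 2:1 weighted average category probability.
- Scenario 1: V = 10.96 × (1 − 0.480) = 5.70; 0.693 × √5.70 = 1.655; Φ(0.619) = 73.2%.
- Scenario 2: V = 10.96 × (1 − 0.353) = 7.09; 0.693 × √7.09 = 1.846; Φ(0.809) = 79.1%.

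Simulating the tie-corrected Mann-Whitney test gives 74.2% and 80.9% from the Table 2 proportions, and 74.9% and 80.3% at an exact OR of 2. The stated 74% and 80% are reproduced. A two-sided 0.15 test would give 60.5% and 68.6%.

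**2. Size of a chance imbalance.** SD of the difference in mean score = √[variance × (1/100 + 1/50)].
- Three levels: variance 0.61, SD = √(0.61 × 0.03) = 0.135 points.
- Four levels: variance 0.7875, SD = √(0.7875 × 0.03) = 0.154 points.

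A difference beyond 1 SD in one given direction has probability about 0.16, or 1 trial in 6.

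**3. Power, score ignored → used.** Three-level score, treatment OR 2 within each level, van Elteren test stratified by score:

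| OR per point | Scenario 1 | Scenario 2 |
|---|---|---|
| 1.25 | 75.0 → 74.6% | 80.4 → 80.1% |
| 1.5 | 74.3 → 74.3% | 79.4 → 79.7% |
| 2 | 72.7 → 73.9% | 77.4 → 79.1% |
| 3 | 68.4 → 72.4% | 72.8 → 77.6% |

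Rank analysis of covariance on the four-level score, with the marginal OR held at 2, gives gains of similar size: 74.6 → 75.1% and 79.5 → 80.1% at OR 1.5; 74.0 → 76.2% and 78.3 → 80.6% at OR 2. If the score has no prognostic value, power is 74.9% against 74.8% in Scenario 1 and 80.1% for both tests in Scenario 2.

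**4. False-go rate.** Over all null trials it is about 15% with or without the score. Given an imbalance of z SDs favouring plasma, the unadjusted rate is approximately Φ[(ρz − 1.036) / √(1 − ρ²)], where ρ is the correlation between score and severity rank. For Scenario 1 at OR 2 with the three-level score, ρ = 0.26 fits:
- z = 1: Φ[(0.26 − 1.036)/0.966] = Φ(−0.80) = 21% (simulated 20.8%).
- z = 1.96: Φ[(0.51 − 1.036)/0.966] = Φ(−0.545) = 29% (simulated 29.9%).

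Averaged over all null trials beyond 1 SD in plasma's favour, the unadjusted rate is about 21-22% at OR 1.5 and 26-30% at OR 2, across both score distributions. Using the score holds it at about 14-16%. Beyond 1 SD in the other direction, the unadjusted rate falls to about 9-10% at OR 1.5 and 6% at OR 2 (four-level score).

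**5. Two limits.**
- *PCR clearance.* Steps 3 and 4 let the score act at every cut-point, including PCR negative against positive, which is the main split in Scenario 2. If it acts only on hospitalization or worse, Scenario 2 power is 80.3 → 80.2%, 80.8 → 80.5% and 80.0 → 79.9% at OR 1.5, 2 and 2.5, and the conditional false-go rate is 15-17%.
- *Oxygen at score 0.* Suppose 15% of entrants are on oxygen with score 0 and have an OR of 4 for worse severity against score 1. Adjusting for the raw score alone then gives almost no power gain and leaves the false-go rate at 21-25% under prognostic imbalance. Score plus an oxygen indicator gains about 1 to 2 points and returns the rate to about 14-16%.

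The adjusted simulations did not include the four steroid-by-vaccination strata. Without covariates, two or four strata leave power at 74-75% and 80-81%.

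**The case against.** The strongest reply is that nothing here is invalid. Randomization keeps the false-go rate at its nominal level, the stated power reproduces without the score, and the final analysis plan is still open. All of that stands.

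A reader might infer that leaving the score out roughly doubles the trial's false-go rate. The documents do not support that. The overall rate is 15% either way. A rate near 30% needs a score OR of about 2 or more per point, which is assumed, and an imbalance beyond 1 SD in plasma's favour; the opposite imbalance lowers the rate. At OR 1.5 the rise is to about 22%. If the score predicts severe illness but not viral clearance, Scenario 2 shows almost no effect.

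A reader might also take 1 point as the minimum for entry and treat the score as a ready-made risk ranking. Item 6 lets oxygen recipients in with 0, so some of the sicker entrants can sit at the bottom of the scale. That objection defeats adjustment for the raw score alone, but not adjustment for the score with oxygen or severity status.

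The open analysis plan does not settle the matter. The adjusted analysis that Section 3.2 defers follows its mention of adjusted P values for pooling Phase 2 with Phase 3, so it does not promise covariates, and the primary test is already named without any.

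**Conclusion.** The point holds in a modest form. A baseline prognostic measure that the protocol requires for every entrant, and whose age and cardiopulmonary components it adjusts for elsewhere, is left out of the one decision that matters. The test remains valid. The cost is some power (about nil at OR 1.5 per point or less, 1 to 2 points at OR 2, 4 to 5 at OR 3) and a go/no-go result more exposed to chance imbalance in an unlucky trial. Every one of these sizes rests on an assumed score distribution and prognostic strength, and the Scenario 2 figures also rest on the score predicting PCR status. The change is worth making because it is nearly free, not because the design is unsound.

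**What to change.** In Section 3.2, or in the final analysis plan before unblinding:

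- Keep the one-sided 0.15 rule and make the primary stratified rank test covariate-adjusted. Use either a stratified rank analysis of covariance or the treatment test from a proportional-odds model containing the stratification factors. Choose one and name it; a short simulation with the actual strata would confirm its operating characteristics.
- Name the covariates: the Section 2.3.1 item 6 score, together with baseline supplemental-oxygen status or the baseline severity rating. Do not enter the score alone. Specify a pre-infusion value, since Section 4.3 lists the Day 0 rating after product administration.
- Name the strata of the test and reconcile them with Sections 2.3.5 and 3.3. Enter risk as a covariate rather than as further strata: three score levels within four strata would make 12 cells, averaging 150/12 = 12.5 participants.
- Report the unadjusted stratified test as supportive.

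The cost is a few sentences and one extra modelling step. No new patients or visits are needed; the database must keep the score total, not just the eligibility result. If the covariates are not prognostic, the power cost is negligible: 0.1 point with rank analysis of covariance. Stratifying by score instead cost 0.3 to 0.4 points at OR 1.25.
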